CASE
COMPREHENSIVE
CANCER CENTER

A Cancer Center Designated by the
National Cancer Institute

STUDY NUMBER: CASE 1816

Protocol Date: 03/29/2016

STUDY TITLE: Intra-operative Assessment of Cavernosal Nerve Stimulus Threshold

PRINCIPAL INVESTIGATOR: [name]

PRINCIPAL INVESTIGATOR: [name]
Department of Urology
Glickman Urological and Kidney Institute
Cleveland Clinic
[name]
[contact] | [contact]

CO-PI: [name], MS
Department of Urology
Glickman Urological and Kidney Institute
Cleveland Clinic
[name]
[contact] | [contact]

[name], MBA
Department of Urology
Glickman Urological and Kidney Institute
Cleveland Clinic
[name]
[contact] | [contact]

STATISTICIAN: Not Applicable (Co-Investigator Managed)

STUDY COORDINATOR: Not Applicable (Co-Investigator Managed)

SPONSOR: Department of Urology
Glickman Urological and Kidney Institute

Cleveland Clinic

SUPPORT/FUNDING:

Department of Urology
Glickman Urological and Kidney Institute
Cleveland Clinic

SUPPLIED AGENT(S):

None

IND #:

None

OTHER AGENT(S):

None

SUMMARY OF CHANGES

Protocol Date	Section	Change
03-29-16		Initial CASE CCC PRMC Submission per CCF IRB Requirement

STUDY SCHEMA

Patients will be randomly assigned to a cavernosal nerve electrical stimulation testing algorithm of 4 different stimulus patterns in sequence (Table 1) while intercavernosal pressure is recorded to detect penile erection. Specifically, a fixed frequency and pulse width will be set with amplitude started at 1 mA and increased by 5 mA increments, to a maximum of 30 mA or until intracavernosal pressure is observed to persistently rise. Upon pressure rise, amplitude will be decreased by 5 mA and then increased by 1 mA increments to identify the threshold level. If no pressure changes are appreciated, the contralateral neurovascular bundle will be assessed, and if no pressure changes are observed here, the procedure will be aborted.

Table 1: Stimulus Parameter Testing Algorithm

Stimulus Pattern	Frequency	Pulse Width	Amplitude (Variable)
1	10 Hz	100 μ s	1 mA to 30mA
2	10 Hz	200 μ s	1 mA to 30mA
3	7 Hz	100 μ s	1 mA to 30mA
4	7 Hz	200 μ s	1 mA to 30mA

PROTOCOL SUMMARY

Protocol Number/Title	CASE 1816
Study Phase	Pilot
Brief Background/Rationale	Erectile dysfunction persists in approximately 80% of men 1 year after prostatectomy. Various erectile rehabilitation strategies have not provided benefit. Electrical stimulation has been demonstrated to benefit neuroregeneration and the functional recovery of neuromuscular systems. Therefore, electrical stimulation of the cavernosal nerves during radical prostatectomy is being investigated for its potential development into a treatment aimed at improving recovery of erectile function after prostatectomy. This pilot study is intended to determine the threshold of electrical stimulation that results in penile erection, as defined by persistent intracavernosal pressure increase, such that future studies of sub-threshold stimulation may be pursued.
Primary Objective	Endpoint for this study is the accrual of 7 patients and collection of cavernosal nerve stimulation thresholds for induction of penile erection in each.
Secondary Objective(s)	None
Exploratory Objective(s)	None
Correlative Objective(s)	None
Sample Size	7 men age 18 years or older
Disease sites/Conditions	Prostate cancer being treated with radical prostatectomy.
Interventions	Unilateral cavernosal nerve electrical stimulation, possible contralateral cavernosal nerve electrical stimulation, and intracavernosal pressure recording.

ABBREVIATIONS

CCCC	Case Comprehensive Cancer Center
CRF	Case Report Form
FDA	Food and Drug Administration
ICF	Informed Consent Form
IRB	Institutional Review Board
PRMC	Protocol Review and Monitoring Committee
SOC	Standard of Care
CCF	Cleveland Clinic Foundation

TABLE OF CONTENTS

1.0 Introduction

1.1 Erectile Dysfunction after Prostatectomy

Erectile dysfunction persists up to 1 year after radical prostatectomy in approximately 70% to 80% of cases, whether performed with open or robotic surgical approaches (O'Neil 2016). Approximately 30 years ago, it was identified that intraoperative preservation of the prostatic neurovascular bundles containing the cavernous nerves enabled some men to recover and maintain erectile function after surgery (Lepor 1985). Prior to this discovery, the surgery essentially had a 100% rate of erectile dysfunction.

Since that time, technologic advances in pelvic surgery, such as robotic surgery, have demonstrated a minimal advantage over open surgery in terms of postoperative erectile dysfunction rates. Furthermore, there is limited data to suggest current postoperative penile rehabilitation therapies provide a marked improvement in erectile function recovery after pelvic surgery. One temporal analysis found stable rates of erectile dysfunction, at 70% to 90%, from the mid-1990s through the current era (Schauer 2015). A contemporary analysis of patient-reported outcomes confirms that 78% to 88% of men demonstrate some degree of erectile dysfunction after prostatectomy (O'Neil 2016).

1.2 Cavernosal (Cavernous) Nerve Electrical Stimulation

1.2.1 Preclinical Data: Electrical Stimulation and Nerve Regeneration

Electrical stimulation elsewhere in urology, specifically the sacral and pudendal nerves, has been applied with permanently implanted devices, and used successfully to treat voiding dysfunction. Laboratory studies have shown that temporary pudendal nerve stimulation in animal models of incontinence can improve neuroregeneration by increasing neurotrophin levels within the nerve, a phenomenon observed in other peripheral nerves (Jiang 2013). This beneficial effect of temporary nerve stimulation, and the practice of urologic patients treated with nerve stimulators undergoing temporary percutaneous test stimulation before implantation, led to our overall hypothesis for a long-term series of clinical studies: temporary percutaneous stimulation of the cavernous nerves after prostatectomy will improve neuroregeneration, and the subsequent postoperative recovery of postoperative erectile function, as defined by a reduced erectile dysfunction rate, better quality of erections, shorter time to functional recovery, and improved patient satisfaction.

The stimulation assessed in the animal models of pudendal nerve recovery was performed with sub-threshold (20 Hz frequency, 0.3 mA amplitude, 100 μ s pulse width) parameters, which did not result in end-organ activation (anal sphincter contraction). The ideal application of electrical stimulation to facilitate recovery of erectile function will similarly utilize sub-threshold (i.e. stimulation parameters will not result in an erection) parameters. Previous work during intraoperative cavernous nerve mapping studies confirmed the ability of intraoperative stimulation (20 Hz frequency, 1-10 mA amplitude, 220 μ s pulse width) to produce erections (Rehman 1999). However, the stimulus

thresholds at which sub-threshold stimulation became supra-threshold stimulation are unknown.

1.2.2 Clinical Data: Cavernosal Nerve Stimulation for Anatomic Localization

The use of electrical stimulation has been applied to prostatectomy for the purpose of cavernous nerve localization to facilitate their anatomic preservation. Commercially available devices for this purpose have been developed; however, current surgical approaches and improved understanding of pelvic anatomy have resulted in intraoperative electrical stimulation providing no advantage in preserving the prostatic neurovascular bundles and cavernous nerves. The implantation of permanent electrodes for stimulating (20 Hz frequency, 5mA - 60 mA amplitude, 260 μ s pulse width) the cavernous nerves to produce erections has been investigated, but this has never gone beyond initial clinical trials (Burnett 2008).

1.3 Study Rationale

Various laboratory studies have investigated using biologically active molecules to facilitate neuroregeneration of the cavernous nerves. These include various growth factors, such as neurotrophins, as well as the use of stem cells. While animal models have shown some promise with these, the clinical investigation of such treatments has been limited by their unknown systemic effects and other potential adverse risks they pose. These challenges highlight the potential for application of non-biologic therapies, such as electrical stimulation, to augment neuroregeneration. Electrical stimulation, which has been demonstrated safe and well tolerated in many other human applications, has been shown to enhance neuroregeneration. As cavernosal nerve electrical stimulation can result in penile erection, determining sub-threshold stimulation parameters is necessary such that men can undergo stimulation after surgery and not develop penile erection with an indwelling foley catheter. This will facilitate both their comfort and social acceptance of the treatment.

2.0 Objectives

2.1 Primary Objective

To determine the cavernosal nerve electrical stimulation amplitude thresholds at which an erection, as indicated by persistent increases in intracavernosal pressure, occurs for various stimuli of fixed frequency and fixed pulse-width.

2.2 Secondary Objective

There are no secondary objectives of this study.

3.0 Study Design

3.1 Prospective Pilot Study

This is a prospective pilot study used to determine a threshold range of cavernosal nerve electrical stimulation parameters that result in penile erection. Assignment to the order of stimulation paradigms will be randomized. No placebos are used. No blinding is used.

3.2 Number of Subjects

This study will enroll a total of 7 men, over age 18, who are undergoing prostatectomy for prostate cancer.

3.3 Replacement of Subjects

If men do not respond to intraoperative electrical stimulation, as evidenced by intracavernosal pressure increase, they will not be replaced. These men will be deemed non-responders. If men opt out of stimulation preoperatively, they will be replaced. If the cavernous nerves are sacrificed intraoperatively, these men will be replaced. In total, only 7 men will undergo stimulation testing.

3.4 Expected Duration of Treatment and Subject Participation

Treatment will be performed intraoperatively and take approximately 20 to 30 minutes. Thereafter, patients will be monitored as part of standard care, for approximately 24 hours postoperatively. Following this, they will be reassessed at the standard postoperative outpatient follow-up visit approximately 7 to 21 days after prostatectomy.

4.0 Subject Selection

Each of the criteria in the sections that follow must be met in order for a subject to be considered eligible for this study. Use the eligibility criteria to confirm a subject's eligibility.

4.1 Inclusion Criteria

Subjects must meet all of the following inclusion criteria to be eligible for enrollment:

Below are common examples: Edit per protocol or see further examples hyperlinked above.

___ 4.1.1 Subjects must have prostate cancer being treated via radical prostatectomy by a single surgeon (primary investigator) with planned intraoperative nerve sparing.

___ 4.1.2 Subjects must have intact preoperative erectile function, sufficient for penetrative intercourse without medication nor assistive device, as defined by a SHIM / IIEF-2 score 22 or higher, which is collected as part of routine care.

___ 4.1.3 Age \geq 18 years, as prostate cancer is not routinely treated in children.

- ___ 4.1.7 Subjects must have the ability to understand and the willingness to sign a written informed consent document.

4.2 Exclusion Criteria

The presence of any of the following will exclude a subject from study enrollment.

- ___ 4.2.1 Baseline erectile dysfunction, as defined by the use of medications or devices to assist erection, lack of baseline erections, or a SHIM / IIEF-2 21 or lower, which is collected as part of routine care.
- ___ 4.2.2 Lack of successful intraoperative nerve sparing.
- ___ 4.2.3 Neurologic, metabolic, or vascular diseases that may negatively impact erectile function, such as: diabetes mellitus, peripheral vascular disease, coronary artery disease, stroke, multiple sclerosis, parkinson's disease, multiple systems atrophy, epilepsy, or spinal cord injury.
- ___ 4.2.4 Inability to provide a fully informed consent.

4.3 Inclusion of Women and Minorities

Men of all races and ethnic groups are eligible for this trial. Women are not eligible due to the lack of a prostate and penis.

5.0 Registration

All subjects who have been consented are to be registered in the OnCore™ Database. For those subjects who are consented, but not enrolled, the reason for exclusion must be recorded.

All subjects will be registered through Cleveland Clinic and will be provided a study number by contacting the study coordinator listed on the cover page.

Subjects will be randomized to the order of the four stimulus paradigms being studied.

6.0 Treatment Plan

6.1 Treatment Regimen Overview

All cavernous nerve electrical stimulation patterns (labeled 1 – 4 in Table 1) will be tested in each patient in a randomized order.

Table 1: Stimulus Parameter Testing Algorithm

Stimulus Pattern	Frequency	Pulse Width	Amplitude (Variable)
1	10 Hz	100 μ s	1 mA to 30mA
2	10 Hz	200 μ s	1 mA to 30mA
3	7 Hz	100 μ s	1 mA to 30mA
4	7 Hz	200 μ s	1 mA to 30mA

Treatment will only be administered intraoperatively.

Appropriate dose modifications for the Electrical Stimulation are described in Section 7.0.

Reported adverse events and potential risks of Electrical Stimulation are described in Section 8.0.

There are no restrictions on other investigational or commercial agents or therapies that may be administered with the intent to treat the subject.

6.1.1 Electrical Stimulation

In addition to a dosing schema, please add a narrative description of the investigational agent administration.

Investigational Agent Administration

Subjects will receive stimulation patterns 1 – 4 in a randomized order. Specifically, a fixed frequency and pulse width will be set with amplitude started at 1 mA and increased by 5 mA increments, to a maximum of 30 mA or until intercavernosal pressure is observed to persistently rise. Upon pressure rise, amplitude will be decreased by 5 mA and then increased by 1 mA increments to identify the threshold level.

If no response is observed on the cavernosal nerve assessed, the contralateral cavernosal nerve will be tested with the same stimulus pattern. If no response is seen on the contralateral nerve, the procedure will be aborted.

6.2 Electrical Stimulation Dose Escalation

Dose escalation will proceed within each stimulus pattern according to the following scheme. The pulse width and frequency will be fixed. Amplitude started at 1 mA and increased by 5 mA increments, to a maximum of 30 mA or until intercavernosal pressure is observed to persistently rise. Upon pressure rise, amplitude will be decreased by 5 mA and then increased by 1 mA increments to identify the threshold level.

If no response is observed on the cavernosal nerve assessed, the contralateral cavernosal nerve will be tested with the same stimulus pattern. If no response is seen on the contralateral nerve, the procedure will be aborted.

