6.3 Definition of Dose-Limiting Toxicity (Applicable for dose escalation studies only)

No dose-limiting toxicities are anticipated in this study. The ranges of electrical stimulation that will be tested have been proven safe and effective in prior work on intraoperative cavernosal nerve stimulation for anatomic mapping.

Management and dose modifications are outlined in Section 7.

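### As written, one stimulus pattern that fails on both nerves ends testing, so a man who would respond to another pattern can lose obtainable thresholds or count as an unreplaced non-responder

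*Combined protocol and SAP*

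**What the plan says.** Section 6.1 states that the four patterns in Table 1 (10 or 7 Hz, each with 100 or 200 microseconds, 1 to 30 mA) "will be tested in each patient in a randomized order".

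Section 6.1.1 says that when the first nerve does not respond, "the contralateral cavernosal nerve will be tested with the same stimulus pattern". Sections 6.1.1 and 6.2 then give the same consequence: "If no response is seen on the contralateral nerve, the procedure will be aborted". The Study Schema has a similar rule, "if no pressure changes are observed here, the procedure will be aborted", without saying that the contralateral test uses the same pattern. None of these places has a step that tries the remaining patterns.

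Section 3.3 covers men without a pressure rise: "These men will be deemed non-responders". They are not replaced, and only 7 men are stimulated.

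Section 6.3 says the ranges to be tested "have been proven safe and effective in prior work on intraoperative cavernosal nerve stimulation for anatomic mapping", but gives no settings. The settings in the background are "20 Hz frequency, 1-10 mA amplitude" with 220 microseconds (Section 1.2.1, mapping) and "20 Hz frequency, 5mA - 60 mA amplitude" with 260 microseconds (Section 1.2.2, implanted electrodes).

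**The concern.** Stopping after one pattern is sound only if every single pattern is known to work in an intact nerve. If that is not known, a failed pattern may mean a nerve that does not respond or a pattern that is too weak for that man at 30 mA, and the rule treats the two alike. The order is randomised, so chance decides which of his other thresholds are lost. If the failing pattern comes first, he has no threshold at all, fits the Section 3.3 description of a non-responder, and is not replaced.

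The trial's only product is a set of amplitude thresholds in 7 men, at most 7 × 4 = 28, summarised descriptively under Section 14. No later analysis step would restore thresholds that were never measured or separate the two kinds of non-response.

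**Working it through.** **1. Do the documents show that each pattern works?** Table 1 uses 7 or 10 Hz and 100 or 200 microseconds. The two settings given for producing erections use 20 Hz and 220 or 260 microseconds. Neither frequency nor pulse width overlaps, and the tested values are lower on both. The amplitude cap works the other way. Charge per pulse is mA × microseconds / 1000, in microcoulombs; charge per second multiplies this by the frequency.

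| Setting, at maximum amplitude | Per pulse | Per second |
|---|---|---|
| Pattern 1 (10 Hz, 100) | 30 × 0.1 = 3.0 | 30 |
| Pattern 2 (10 Hz, 200) | 30 × 0.2 = 6.0 | 60 |
| Pattern 3 (7 Hz, 100) | 3.0 | 21 |
| Pattern 4 (7 Hz, 200) | 6.0 | 42 |
| Mapping (20 Hz, 220, 10 mA) | 10 × 0.22 = 2.2 | 44 |

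All four patterns exceed the mapping maximum per pulse. Three of four fall below it per second. So the documents establish neither that every pattern works nor that any will fail.

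**2. Loss in one man.** Suppose m of his 4 patterns fail on both nerves, and all 24 orders are equally likely. A pattern that would respond is measured only if it comes before all m failing ones. Among those m + 1 patterns each is equally likely to be first, so it is kept with probability 1/(m+1). Expected loss is (4 − m) × m/(m+1). No threshold is obtained if a failing pattern comes first, with probability m/4. Enumerating the 24 orders gives the same results.

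| m | Obtainable | Mean lost | Chance of none |
|---|---|---|---|
| 0 | 4 | 0 | 0 |
| 1 | 3 | 1.5 | 1/4 |
| 2 | 2 | 1.33 | 1/2 |
| 3 | 1 | 0.75 | 3/4 |

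**3. Loss in the trial.** If j of 7 men each fail m patterns, 28 − jm thresholds are obtainable and 4(7 − j) + j(4 − m)/(m+1) are expected. The documents give no failure rates, so j and m are assumptions.
- j = 2, m = 2: 20 + 2 × 2/3 = 21.3 of 24. Expected men who would respond but yield nothing: 2 × 1/2 = 1.
- j = 4, m = 2: 12 + 4 × 2/3 = 14.7 of 20. Expected such men: 2.

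If instead one pattern fails independently with probability q in each man, the chance of at least one such man among 7 is 1 − (1 − q/4)^7. This is 0.16, 0.30, 0.42 and 0.61 for q = 0.10, 0.20, 0.30 and 0.50.

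**4. Which end of the range moves?** A simulation of 7-man trials assumed a pattern 2 median of 5, 10 or 15 mA, between-man log SD 0.5, error log SD 0.1, thresholds × 1.43 at 7 Hz and × 1.5 at 100 microseconds, and failure above 30 mA. The comparator goes past a failed pattern (pattern 2 next, stopping if that fails too), with no time limit. Cells show abort v comparator.

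| Median | Thresholds obtained | Mean largest, pattern 2 (mA) | Mean smallest, pattern 2 (mA) |
|---|---|---|---|
| 5 | 27.6 v 27.8 | 9.9 v 10.4 | 2.64 v 2.64 |
| 10 | 22.9 v 25.0 | 15.6 v 19.1 | 5.34 v 5.34 |
| 15 | 15.7 v 19.7 | 18.5 v 23.4 | 7.95 v 7.92 |

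The upper end falls and the lower end stays put. The sizes depend wholly on the assumed thresholds.

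**5. What a 30-minute stop costs the fix.** Dividing 20 to 30 minutes by 4 patterns gives an assumed 5 to 7.5 minutes per pattern on one nerve, so 10 to 15 for a failed pattern.
- m = 1 at 5 minutes: 10 + 3 × 5 = 25, so all 3 thresholds are kept.
- m = 1 at 7.5 minutes: 15 + 3 × 7.5 = 37.5, so whatever comes last is cut. That is a responding pattern with probability 3/4, leaving 3 − 0.75 = 2.25 of 3, against 1.5 under the abort rule.

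**The case against.** The best reply is that the abort ends only the pattern in hand. Section 6.2 introduces its scheme as one that operates within each pattern, Sections 6.1 and 6.1.1 say every man gets all four, and Section 3.3 speaks of response to stimulation in general. On that reading the sections agree and nothing is lost. The reading is possible, but the sentence says the procedure is aborted, and no text limits this to one pattern. Two teams could follow the protocol differently, so the wording needs changing on either reading.

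It can also be said that stopping after both nerves fail at up to 30 mA is reasonable in a short descriptive pilot in men with good erectile function (SHIM of 22 or more) and spared nerves. The time budget is a fair point, and the fix respects it. Good selection makes failure less likely but does not show that each pattern works.

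A reader might infer more than the documents support:
- *That the patterns are too weak and will fail.* No pattern is shown to fail. At 30 mA every pattern delivers more charge per pulse than the mapping maximum, and 200 microseconds is close to 220.
- *That the sub-threshold range would be wrong.* Later sub-threshold use depends mainly on the low end, which barely moves.
- *That every aborted man loses everything.* Thresholds measured before the abort are kept. He clearly fits Section 3.3 only if a failing pattern came first.
- *That the simulated gains are forecasts.* They rest on assumed thresholds and ignore the time limit.

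**Conclusion.** The concern holds in limited form. Taken literally, the abort rule conflicts with Section 6.1, and together with Section 3.3 it can leave a man who would respond to another pattern as an unreplaced non-responder. The 1/(m+1) retention is exact, given equally likely orders and m failing patterns. How often a pattern fails is unknown, so the loss across the trial could be nil or several of the 28 planned thresholds. What is at risk is the upper end of the range, its completeness, and the meaning of the non-responder count. Section 6.3's assurance does not settle the matter, because the mapping settings the protocol itself reports are not those being tested. With 7 men and no replacement, missing thresholds cannot be recovered later, so a short amendment is worthwhile.

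**What to change.** In the Study Schema, 6.1.1 and 6.2, replace the abort sentence with: *If neither nerve responds by 30 mA, record >30 mA for that pattern and go on to the next pattern in the assigned order; stop at 30 minutes and record any remaining pattern as not tested.*

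Optionally, if no pattern has yet responded, test pattern 2 next (10 Hz, 200 microseconds, the highest frequency and pulse width in Table 1), stop if it also fails on both nerves, and record the actual order. This limits a man who responds to nothing to two failed patterns, about 20 to 30 minutes instead of 10 to 15 on the assumed times. It departs from the randomised order in those men.

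In Section 3.3, define a non-responder as a man with no pressure rise on either nerve for any pattern tested, pattern 2 included. A man with any measured threshold is not a non-responder, so failure of pattern 2 alone must not decide the label. In Section 14, report for each pattern the number measured, the number >30 mA and the number not tested.

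The change needs a protocol amendment but no new patient, device or setting. Its cost is some extra intraoperative time inside the stated 20 to 30 minutes. At about 7.5 minutes per nerve the time limit leaves some patterns untested, so not all lost thresholds come back.
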